### VII. Biological/Medical Assessments

To assess safety-related issues, the following will be obtained from subjects: BAC (using an alcohol breathalyzer), urine drug screens at screening session and before each MRI test, urine pregnancy tests for all biological females of child bearing potential (before the fMRI scans only), blood chemistries and hematology at screening session and last treatment session, body weight and BMI, vital signs, ETG (screening and sessions 1, 4, 8, 12, 16), and Peth (pre and post). The Peth is a blood test that is used to detect prolonged or heavy alcohol consumptions within the past 2-3 weeks. The ETG test indicates the level of ethanol in urine for 1-3 days after ingestion. Most assessments will be obtained at the baseline assessment and following the Assessment Schedule. If a participant has abnormal results after analysis of the medical assessments, more tests will be ordered to ensure the safety of the participants.

Note: As of March 18th, 2020, due to remote procedures, urine and blood sample have been reduced to being collected only on screening session and after last treatment session, at a Quest Diagnostics facility. The only exception is when a participant comes in-person for an fMRI, in which a urine sample is collected for pregnancy and drug testing.

Balloon Analogue Risk Task: The Balloon Analogue Risk Task will be administered at session 1 and the last treatment session. In this online task, participants are presented with a balloon. Clicking a button will pump the balloon, causing it to inflate and the participant to be awarded a certain amount of money. This happens until a threshold is reached and a pump will cause the balloon to explode, leading to loss of all money earned. At any point in time, participants can choose between pumping the balloon further, or not pumping the balloon and collecting the money they have already earned. 90 trials are conducted and the average number of pumps delivered are used to measure levels of risk-taking (Lejuez et al., 2002).

Rogers Risk Task: The Rogers Risk Task will be administered at session 1 and the last treatment session. In this online task, participants are assigned a certain number of points to begin with and are instructed to make decisions that will increase their total score. They are then presented with tasks that involve gambling their points. For example, they are presented with red and blue boxes and told that one box contains a yellow ticket. If they choose a red box that has a yellow ticket, they will gain 30 points, but if they choose a red box that does not have the yellow ticket, they will lose 30 points. If they choose a blue box that has the yellow ticket, they will gain 70 points, but if they choose a blue box that does not have the yellow ticket, they will lose 70 points. Participants' speed of decision-making and choice are used to measure their willingness to take risks (Rogers, 1999).

Paced Auditory Serial Addition Test (PASAT): The PASAT is a measure of cognitive function that assesses auditory information processing speed and flexibility, as well as calculation ability (Gronwell, 1977). The PASAT is presented using a computer software called Inquisit. Single digits are presented every 3 seconds and the participants must add each new digit to the one immediately prior to it. Shorter inter-stimulus intervals (e.g., 2 seconds or less) have also been used with the PASAT but tend to increase the difficulty of the task. Administration time is approximately 10-15 minutes, including practice sessions. The PASAT has demonstrated high split-half reliability and evidence for convergent and divergent validity (Gronwall & Sampson, 1974).

The Dot Probe Task: Two **dot-probe** tasks (500ms stimulus presentations) will be used to measure attentional bias towards and away from negative stimuli. The **Neutral-Threat (NT) Words** is the first task, which uses general anxiety and depression-related stimuli developed by MacLeod, Mathews, and Tata (1986) using a protocol developed by Bar-Haim and colleagues (2010). The second task is **Neutral-Threat-Happy (NTH) Faces**, a face-based task which displays faces with angry, happy, and neutral expressions from the MacArthur Network Face Stimuli Set. This task uses the protocol devised by Bar-Haim and colleagues (TAU-NIMH ABMT Initiative, 2012).

*Emotion Conflict Task* (Etkin et al., 2010; Etkin & Schatzberg, 2011): This task measures two aspects of cognitive regulation of emotional processing (conflict detection, inhibitory control) by requiring subjects to identify expression of an emotional face (e.g., happy, fearful) while ignoring an emotion word (e.g., "happy," "fear") superimposed on the face.

Montreal Cognitive Assessment (MoCA): The MoCA was designed as a rapid screening instrument for mild cognitive dysfunction. It assesses different cognitive domains: attention and concentration, executive functions, memory, language, constructional skills, conceptual thinking, calculations, and orientation. Time to administer the MoCA is approximately 10 minutes. The total possible score is 30 points; a score of 26 or above is considered normal (Nasreddine et al., 2005).

Note: Due to sessions being conducted remotely (including the screening session) as of March 18th, 2020, item one of the Montreal Cognitive Assessment (MoCA) is no longer administered to participants at the screening session. We will score the total score out of 29 instead of 30 to account for the change.

# **Measures of Study Integrity**

Treatment Involvement Form (TIF; adapted from ACAP and LTS study forms): The TIF-TTS edition is a 7-item questionnaire that asks about any changes in medication, treatment, or lifestyle since the last assessment time point. At the beginning of each assessment, with the exception of the Screening Session, the RA administers the TIF to the participant and reviews it after every session. Any changes should be reported to the attending clinician. TIF is designed to assess for whether the participant has sought treatment/services outside of their study therapy sessions. It is used to determine start of treatment and/or change in treatment.

Knowledge of Treatment Form (KNO; as used in Roll et al., 2004): The IEs complete the KNO form before and after the post, 1-month, and 6-month ADIS assessment. The main functionality of the KNO is to determine whether the blind has been broken during the post assessment, or any other time leading up to the assessment. Roll et al. (2004) suggest that study integrity should try to be maintained by having evaluators who are blind to treatment condition to prevent any biases. The current version of the KNO is a 3-item questionnaire that asks the evaluator to guess which condition they believe the participants is in and how confident they are that the participant is in

that condition on a 0 to 8 Likert scale (0=Not at all, 4=Somewhat, 8=Absolutely). The last item asks the evaluator to disclose any information that may have contributed to a potential blind break.

### For participants completing the MRI component of the study:

Stroop Task: The Stroop tasks will be shown to subjects using a behavioral experiment software called E-Prime. During the task, neutral words and alcohol-related words will be projected on the screen in different color fonts. Participants will be instructed to press a color button on a button box that corresponds to the color of the font of the word on the screen. There are four colors on the button box, which are red, blue, yellow, and green. The four blocks of stimuli include alcohol-related words (e.g. bar, vodka), color word (e.g. blue, green), and neutral words (e.g. years, minute). There is a practice run of the Stroop task to get participants used to using the button box, which takes about 2 minutes. The Stroop task then follows, which takes about 7 minutes to complete.

Alcohol Cues Task: The Alcohol Cues Task entails the presentation of five sets of images, with both neutral and alcohol-related images. These cues will be shown to subjects using a behavioral experiment software called E-Prime. Subjects will be instructed to look at the images on the screen in the MRI scanner. There are five runs of the task. In the beginning of each run, participant will see "Get Ready" on the screen. There are 22 pictures in each run. In each run, participant will see a fixation cross for a varied amount of time from 6000 milliseconds to 14000 milliseconds followed by the presentation of an alcohol image or a neutral image for 4000 milliseconds. In each run there are 2 images with animals in it. Participants are instructed to press a red button on a button box each time they see an animal that is not a human on the screen. The entire task takes approximately 40 minutes to complete.

*Event-Based Reappraisal Task:* The Event-Related Reappraisal task involves the presentation of color images selected from the International Affective Picture System (Lang, Greenwald, Bradley, & Hamm, 1993). These images will be shown to subjects using a behavioral experiment software called E-Prime. The duration of the task is 10 to 15 minutes. At the beginning of each trial, instructions to either "LOOK" or "DECREASE" will be presented on the screen, then an image will appear in the center of a black screen. Participants will be instructed to view the image, understand its content, and allow themselves to experience/feel any emotional response it might elicit. On LOOK trials, a photo will be shown and participants will be instructed to attend to and be aware of, without attempting to alter feelings elicited by the image. On DECREASE trials, participants will be instructed to reinterpret the image to alter feelings elicited by the image. Participants will rate the strength of current negative affect by pressing a corresponding button on a button box. After pressing the button corresponding to their rating, the number selected will be highlighted on the screen. At the end of the task, a "thank you for participating"

message will be presented. Participants will then be briefed upon completing the task by a study research assistant. The task takes about 12 minutes.

### **Therapist Assessments Procedures**

The therapist is responsible for completing the Homework Compliance Scale (HCS) after each session. For the Take Control condition, there is never assigned HW, and for certain sessions of the UP there is not assigned HW. In these instances the therapist should still complete the HCS and select "0-Homework was not assigned". In addition to completing the HCS every session the study therapist should complete the Working Alliance Inventory-Short Form-Therapist Version (WAI-SFT) at sessions 4, 8, 12, and 16. The Clinical Global Impression-Improvement and Severity Scales (CGI-I and CGI-S) should be completed in Qualtrics at session 1, 4, 8, 12, and 16 (the IEs will complete the CGI and CGs at post-assessment, 1-month, and 6month follow-ups). To complete these assessments the therapist should go into the StAR2 Qualtrics folder and select the session number. Within the session folder there is a Therapist Assessment survey battery which includes all the assessments that need to be completed for each session.

### **Documenting Protocol Deviations**

There are a number of protocol deviations that may occur during treatment: failing to administer key components of the treatment protocol, engaging in treatment procedures (or providing information) that may overlap with another treatment condition, and conducting treatment sessions that take longer than what is specified in the study protocol. A protocol deviation form should be completed and submitted to the IRB when a deviation occurs. The IRB's response to the deviation, and the deviation submission form, should be saved in

When any protocol deviation occurs during treatment, the study staff should note this in the comments/protocol deviation section of the StAR2 Deviation Tracking Log in Google Sheets. If you do not yet have access to this, email the RA and they will grant you access. The RA will then document the deviation and maintain a de-identified note

## Handling Participant Requests for Booster Sessions or Additional Treatment

In general, participants will be asked not to seek additional treatment (including treatment from study therapists) during the follow-up period. In the event that a participant requests additional treatment, study staff may wish to explain the importance of refraining from additional treatment in the context of the research study's aims. It may also be helpful for participants to think about treatment as more of an ongoing process of working on the developed and learned skills that occurs even after the formal program has ended, as opposed to something which has a definitive end-point.

If a participant is planning on seeking additional treatment, contact the Project Director for additional assistance. Treatment engagement during the follow-up period will be assessed at the 1-month and 6-month follow-up assessment and may ultimately be an additional indication of treatment outcome. With that being said, the study therapist should by no means encourage study participants to seek additional treatment during the follow-up period.

At the final follow-up assessment, participants may request additional treatment. Treatment will not be provided as part of the research study, but appropriate referrals should be made. These requests, and any action taken by the IE (or RA), should also be documented as a clinical note. As the frequency of these requests may be used as a clinical outcome variable, they should be carefully documented for later review.

#### **Managing Issues in Treatment:**

#### Alcohol Use

If the participant's BAC is greater than 0.00% before signing the informed consent, he/she/they will have to reschedule the screening, which can be a few hours later (and BAC will be tested again) or another day. If asked to reschedule, the participant will be asked not to drive home and to make other transportation arrangements. If no one is available to take the participant home and he/she/they do not live in an area with public transportation access, a study staff member may call a taxi or car service.

For all other study sessions, participants with BAC levels greater than 0.02% will be asked to remain at the center until their levels reach below 0.02, or reschedule if necessary. Again, if a participant is under the influence and is asked to reschedule the appointment, the participant will be asked not to drive home and to make other transportation arrangements.

Note: Due to sessions being conducted remotely, a session is simply cancelled and/or rescheduled if BAC levels are above threshold.

#### Noncompliance

The following link describes IRB procedures regarding noncompliance: https://www.bu.edu/researchsupport/forms-policies/noncompliance-in-human-subjects-research/

### Management of Life Crises: Determine Severity of Crisis

Major Life Crises include: death of a spouse, child, or parent; major illness or accident to spouse or child. Minor Life Crises include: car accident with physical injury, sudden impending divorce, loss of job, etc.

#### **Major Life Crises:**

If the study staff member defines the crisis as major, one full session can be devoted to a discussion of this event and its impact. The study staff member should then schedule a make-up session within one week to cover the material missed due to the crisis (Note: This would most

likely extend the length of the study by one week and is tantamount to the participant cancelling a study session). If the participant continues to need help in dealing with this crisis, a second session may be used. However, the participant must then be withdrawn from the study and given alternative treatment and/or an outside referral.

### **Minor Life Crises:**

If the therapist defines the crisis as minor, then it does not warrant one full session of discussion. The study staff may spend approximately 15 minutes discussing the event with the participant and then should redirect the participant back to protocol material by acknowledging that such an event is likely to increase feelings of anxiety and probably would occur in anyone experiencing such an event, asking how this event affected the participant and his/her/their anxiety and/or panic, and asking how his/her/their reaction to the crisis can be discussed in the context of treatment.

If the event is not one in which the participant can be easily refocused, or requires more than 10-20 minutes of session time, the therapist should end the session after a brief discussion of the event, and schedule another full session (within a week) to cover the missed UP or TC treatment material.

NOTE: A life crisis and postponement of treatment can only occur once during treatment. If a second crisis emerges that requires postponement of treatment, it can still be addressed during the session. However, these participants will then be removed from study treatment and given alternative treatment or an outside referral.

## **Removal from Protocol Due to a Life Crisis**

As noted above, this might occur if: 1) the participant needs additional support in dealing with the crisis, or 2) A second major crisis occurs during the course of treatment.

NOTE: A question may emerge regarding the severity of a stressor not listed above, or whether to remove a participant from the study. In these cases, the therapist should consult first with the project director. If there is any disagreement between the therapist and project director, the case may be discussed with the PI, who will make the final decision.

## **Premature Study Termination**

Every effort will be made to keep participants in the study. Participants who drop out of or are withdrawn from the trial will be included in the data analysis as described in the Data Analysis Section of the grant. Participants who choose to end treatment prematurely will be followed for the remainder of the trial if they can still reach the post treatment session (session 12 for TC or 16 for UP) within 16 or 21 weeks from the session 1 date, respectively.

The RA should attempt to collect all self-report measures and clinician administered assessments conducted at the major time-points (4, 8, 12, 16, 1-month, and 6-month follow-up) in the event of a drop-out or withdrawal (if the participant is willing and able to continue in this

manner). Self-reports can be emailed to the participants, and the clinician-administered assessments can be conducted over the phone in order to provide flexibility to the participant if unwilling to come in. All of these sessions should be scheduled on the basis of when the last attended treatment session occurred. The payment schedule will resume, with checks issued on session 8, post, and both follow-ups.

RAs can attempt to call participants three times within two weeks after the last communication. If the participant does not call back after all three attempts, or answers/calls back but declines to continue in any capacity, study staff will make no further attempts to contact.

Participants who are withdrawn from the study by the study staff will be offered alternative care or will be assisted to find other providers upon request. It is not necessary to offer alternative treatment to participants who choose to discontinue. Every effort will be made to record reasons for study dropout or withdrawal in the Treatment Termination Form, and the Attrition tab of the Retention Database.

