### When to Withdraw Participants from the Study

There are two primary reasons participants are likely to be withdrawn from StAR2: 1) clinical deterioration or life crises and emergencies, and/or 2) noncompliance with study requirements and procedures.

Removal of participants from the research study should only occur in rare instances. In most cases, participants who are dropped or withdrawn from study treatment will be asked to complete a posttreatment assessment and will then be followed for the remainder of the followup period (beginning from the date of the posttreatment assessment). In those rare instances when a participant is completely withdrawn from the study (upon their request or at the discretion of study personnel), the project director will complete a note detailing specific reasons the participant will not continue in the trial.

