## **Procedures for Handling Treatment Termination**

### **Drop-Outs**

If it becomes apparent that a participant is dropping out of the study, the therapist and/or RA should attempt to contact the participant by telephone to gather more information about the participant's concerns/reasons for considering dropout. Sufficient information should be gathered to complete the Termination Form for the study, study staff can ask the participant if he/she/they is/are willing to come to the clinic for major assessment time point assessments (without completing any additional treatment sessions) at 4, 8, and 12 weeks for UP and 4 and 8 weeks for TC, and a final assessment with the IE (post-treatment). If the participant declines further assessments in person, study staff may offer telephone assessments.

NOTE: The Termination Form should be completed by the study staff member who contacts the participant. RAs please be sure to remind study therapists to document accordingly.

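### The rules for assessing participants after they stop treatment conflict on who is followed and on the date from which visits are counted

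*Combined protocol and SAP*

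**What the plan says.** Three places in the protocol govern assessment after treatment stops.

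- **Premature Study Termination, first paragraph.** Those who choose to end treatment early "will be followed for the remainder of the trial if they can still reach the post treatment session" (12 for TC, 16 for UP) "within 16 or 21 weeks from the session 1 date, respectively".
- **Premature Study Termination, second paragraph.** After a drop-out or withdrawal, "The RA should attempt to collect all self-report measures and clinician administered assessments conducted at the major time-points". The list includes both follow-ups, and the only limit is the participant's willingness and ability. On timing: "All of these sessions should be scheduled on the basis of when the last attended treatment session occurred".
- **When to Withdraw Participants from the Study.** "In most cases, participants who are dropped or withdrawn from study treatment will be asked to complete a posttreatment assessment". They are then "followed for the remainder of the followup period (beginning from the date of the posttreatment assessment". No window is given.
- **Drop-Outs** (under Procedures for Handling Treatment Termination). Staff can offer assessments "at 4, 8, and 12 weeks for UP and 4 and 8 weeks for TC", plus a final post-treatment assessment with the independent evaluator. No window is given, nor any date from which the weeks are counted.

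The first of these sections also says that drop-outs and withdrawn participants enter the analysis as described in the grant's data analysis section. That section is not part of the documents.

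**The concern.** Two staff members could treat the same early stopper differently and both be following the protocol. One could end follow-up because the last session is out of reach; the other could collect every later time-point. One could count the 6-month visit from the last session attended; the other could count it from a posttreatment assessment held weeks later.

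Two things are at stake. If the conditional rule is applied, whether outcomes are observed depends on attendance, which may well be related to drinking and symptoms. And if visits are counted from the point of leaving, a posttreatment or 6-month value from a drop-out belongs to an earlier time since session 1 than the value with the same label from a completer.

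**Working it through.** **Step 1: set the rules side by side.**

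| Text | Who is followed | Starting date |
|---|---|---|
| Premature Study Termination, para. 1 | Those ending treatment, only if the last session is reachable within 16 (TC) or 21 (UP) weeks | Session 1, for the window |
| Same section, para. 2 | All drop-outs and withdrawals who are willing and able | Last attended session |
| When to Withdraw | Most of those dropped or withdrawn; no window | Posttreatment assessment, for follow-up |
| Drop-Outs | Drop-outs who agree; no window | Week numbers, no origin |

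No text says which rule prevails. The first is also hard to apply: someone who has ended treatment will attend no more sessions, so whether they can still reach session 12 or 16 has no clear meaning.

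**Step 2: how far does the window separate the arms?** Inputs (Study Procedures): 12 sessions in 12 to 16 weeks for TC, 16 sessions in 16 to 21 weeks for UP. Slack = window − sessions.

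- TC: 16 − 12 = 4 weeks; ratio 16/12 = 1.33.
- UP: 21 − 16 = 5 weeks; ratio 21/16 = 1.31.

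With k of S sessions attended by week t, the last session is reachable within W weeks if t + (S − k) ≤ W, that is, if t − k ≤ W − S. Lags up to 4 weeks pass in both arms, a 5-week lag passes only in UP, and 6 weeks or more fails in both. If session 1 is taken as week 0, each allowance is one week longer and the difference is still one week.

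**Step 3: how far can visits move?** The documents give no figure to reproduce. Assumptions: weekly sessions, session k at week k − 1, one month = 365.25/12/7 = 4.35 weeks, six months = 26.1 weeks. Completers' follow-ups are counted from the end of treatment, which is week 11 (TC) or 15 (UP) at weekly pace and week 16 or 21 at the limit.

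| | 1-month visit (week) | 6-month visit (week) |
|---|---|---|
| Last session 4, counted from that session | 3 + 4.35 = 7.3 | 3 + 26.1 = 29.1 |
| Last session 8, counted from that session | 7 + 4.35 = 11.3 | 7 + 26.1 = 33.1 |
| TC completer | 15.3 to 20.3 | 37.1 to 42.1 |
| UP completer | 19.3 to 25.3 | 41.1 to 47.1 |

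A person leaving after session 4 is seen at least 37.1 − 29.1 = 8 weeks (TC) or 41.1 − 29.1 = 12 weeks (UP) before completers of the same arm. After session 8 the gaps are at least 4 and 8 weeks.

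**Step 4: test the other reading.** Scheduling on the basis of the last attended session can also mean projecting the remaining weekly sessions forward from it. Post then falls near its planned date and most of the shift disappears. The withdrawal section opens a second route to a shift, because its follow-up clock starts at the posttreatment assessment, but it does not say how soon after stopping that assessment takes place.

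**The case against.** The strongest reply is that the weight of the text favors continued assessment. The second paragraph of Premature Study Termination asks for every major time-point and allows email and telephone, and the withdrawal section calls complete removal rare. That is fair, and it means loss of data follows only if staff act on the first paragraph. But that paragraph is an explicit condition, and nothing overrides it.

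The populations also differ in part: the condition concerns people who choose to stop, while the withdrawal section mainly concerns withdrawal by staff. This narrows the conflict between those two sections, and the phrase about most cases softens it further. It does not remove the conflict between the two adjacent paragraphs, or that with Drop-Outs.

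Some stronger readings are tempting, and the documents do not support them.

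- A reader might infer that the rule causes differential retention by arm. The windows are each arm's ordinary treatment limits, nearly proportional to session number, and no drop-out rates are given.
- A reader might infer that the primary comparison is biased. It uses treatment-period data (Data Analysis Aims), and drinking comes from the TLFB, a retrospective daily calendar whose values can be placed by date whenever the interview occurs. What remains there is ordinary missing data for anyone not interviewed again.
- A reader might take the Drop-Outs weeks as a third timing rule that differs by arm. They largely repeat the ordinary schedule for 16 and 12 sessions, and without an origin no conflict of starting date can be established.
- A reader might assume that early leavers have their posttreatment visit almost at once. No text says so.
- The calendar difference between TC and UP completers comes from the 12- versus 16-session design, not from these rules.

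**Conclusion.** The conflict is real and can be checked from the text alone: one paragraph makes follow-up conditional, three other statements do not, and two different starting dates are named for the follow-up visits. The possible shift in the 6-month visit is at least 8 weeks (TC) or 12 weeks (UP) for someone leaving after session 4. That size assumes weekly sessions and a literal count from the last session; an early posttreatment assessment under the withdrawal section would cause a similar shift, and under forward projection most of it disappears. The outcomes mainly exposed are clinician ratings, self-report scales and the 1- and 6-month visits. How drop-outs' data enter the models cannot be judged, because that is left to the grant. This is an inconsistency to repair because it risks missing and mistimed outcomes, not evidence of a biased treatment effect.

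**What to change.** 1. Delete the condition about still reaching the last session, so that the second paragraph of Premature Study Termination covers every randomized participant who is willing to be assessed.
2. State one starting date. Early stoppers are assessed on the dates that their own arm's planned schedule would have given, counted from session 1, with post at that arm's planned end of treatment and the 1- and 6-month visits counted from that date. The documents give treatment length as a range, so write the planned end as a single date, for example at weekly pace.
3. Align When to Withdraw Participants from the Study and Drop-Outs with this rule, and give the week numbers in Drop-Outs an origin.

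Leave the completers' schedule as it is, and do not impose the same weeks on both arms. That would move visits now tied to the end of treatment for everyone, which is a redesign that this problem does not require. The change concerns outcome collection only, not when treatment stops.

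The cost is protocol wording and some additional remote assessments. Premature Study Termination already allows email and telephone, and Drop-Outs allows telephone.
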